G3 Analysis Plan

All primary analyses for efficacy will be performed on an intention-to-treat basis. All subjects will be analyzed according to their group assignment regardless of actual treatment received. In addition, both groups will be compared for safety at the end of the study by comparing adverse events and rates of adverse events. In the safety analysis, subjects will only be included if they actually received treatments in that group. (i.e. if a patient on the EPO arm did not get EPO, they should not be included in the analysis of safety in that arm).

G4 Statistical Methods

All data will only be gathered during the period in which the subjects will be active in the study (from baseline to 14 weeks post initial injection).

For the primary aim, we will compare the number of blood transfusions (one 10 ml/kg aliquot = 1 transfusion) between the two groups with a two-proportion z test. With $n = 20$ subjects per group, this test will have 80% power at the $\alpha = 0.05$ significance level to detect a difference. The primary aim will be assessed when all subjects have completed week 14.

We will compare weight gain and the change in oxygen saturation between baseline measurements and the 6 week follow-up with a two sample t-test. We will also use a linear mixed effects model, with a random intercept included to account for within subject correlation, to determine differences in the longitudinal trends in weight and oxygen saturation between groups. The length of the initial stay will be compared between groups with a two-sample t-test. We will treat the number of re-admissions (in regards to failure to thrive and cyanosis) as a categorical variable, and use Fisher's exact test to determine if there is a difference between EPO and control group readmission counts. We will consider the Mann-Whitney U test as a robust alternative to the two-sample t-test if the assumptions of the t-test are not met by the data.

With a sample size of $n = 20$ subjects per group, the t-tests described above will have 80% power at the $\alpha = 0.05$ level to detect an effect size equal to 0.91 times the common standard deviation. For weight change, assuming that the standard deviation of weights at baseline and the 6 week follow-up equal 1.22 and 1.53 (respectively), and assuming a

moderately high correlation between weight measurements within child of $\rho = 0.70$, this translates to a detectable difference of 1.00 kgs.

G5 Missing Outcome Data

As this study will have an intention to treat model, missing outcome data will default to reflect that the subject has received a transfusion. In addition, there may be additional analysis only reflecting subjects who have completed the study in its entirety.

H Data Handling and Record Keeping

H1 Confidentiality and Security

All data will be kept secure through the UCSD REDCap database provided by the Clinical and Translational Research Institute. REDCap is a customizable secure Web based database. It can only be accessed with a username and password that is assigned specifically to each research member. Information entered into the data entry system will be by subject study I.D. number. Data will be checked by an automated validation tool on REDCap to ensure proper data entry. A project has been created in that database for this particular study.

H2 Training

Before the study is started, each member must complete certification requirements to conduct research and show demonstration of familiarity with study procedures, methods for endpoint measurement, use of the database management system to conduct the study.

H3 Case Report Forms and Source Documents

The case report forms (both inpatient and outpatient) will be used as the source documents. The case report form that will be used can be found in section L3.

H4 Records Retention

All data will be kept secure through the UCSD RED Cap database. Hard copies of the case report forms will be stored in binders that will be kept in secure areas in the research office.

I Study Monitoring, Auditing, and Inspecting

I1 Study Monitoring Plan, Auditing and Inspecting

Interim monitoring will be performed as outlined in section G2. In addition, throughout the entire study, data will be collected and compiled on a weekly basis. Data will be entered into the database at least monthly. The research team will review to ensure that the data is being obtained properly, entered into the database properly and to look for any missing data at least quarterly. A safety report will be submitted to the DSMB for review at least quarterly.

J Study Administration

J1 Organization and Participating Centers

University of California, San Diego
Rady Children's Hospital, Heart Institute

J2 Funding Source and Conflicts of Interest

This study is currently funded by the Academic Enrichment Grant from the Rady Children's Hospital foundation.

J3 Committees

Research team:

[name] – Principal Investigator (attending cardiologist/intensivist at RCHSD) – responsible for recruitment, data collection and analysis, as well as manuscript preparation.

[name] (Attending cardiologist at Children's Hospital of Pittsburgh) – will assist in analysis of deidentified data and manuscript preparation.

[name] (Attending cardiologist at Children's Hospital of San Antonio)– will assist in analysis of deidentified data and manuscript preparation.

[name], PhD (attending cardiologist at RCHSD)– will assist in recruitment therapy administration, in data collection, analysis, and manuscript preparation.

[name] RN, MSN, ACNP- (Nurse Practitioner at RCHSD) – will assist in recruitment, therapy administration, in data collection, analysis, and manuscript preparation.

[name] (Attending neonatologist at RCHSD) -- will assist in recruitment therapy administration, in data collection, analysis, and manuscript preparation.

[name] (Pediatric Resident, UCSD) –will assist in recruitment, therapy administration, data collection, analysis and manuscript preparation.

[name], MS – Research Coordinator – responsible for all regulatory/IRB documents and communications pertaining to the study.

J4 Subject Stipends or Payments

There is no stipend or monetary benefits to the patient or their families.

J5 Study Timetable

This study is projected to take 4 years. 2 to 2.5 years for recruitment of study subjects and obtain all necessary data. 1.5 to 2 years for statistical analysis and manuscript preparation.

K Publication Plan

After the study and analysis is complete, we plan to publish the data to a journal that is well recognized in the field of congenital heart disease.

L Attachments

L1 Tables

**Table 1
 Treatment Group**

Tests and Procedures	Baseline (one week post op/cath, ≤ 48 hours prior to 1 st injection)	Week 1 (1 week post op)	Week 2*	Week 3*	Week 4*	Week 5*	Week 6*	Week 7*	Week 14
Review eligibility	X								
Informed Consent	X								
Physical Exam including Saturation	X	X	X	X	X	X	X	X	X
Epogen Injection		X	X	X	X	X	X		
Iron		X and ongoing for 12 weeks							
CBC Lab Draw	X		X	X	X	X	X	X	X
Iron Studies	X		If needed after iron replacement therapy						X

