Transfusions are currently the treatment of choice for clinically significant anemia in the cyanotic congenital heart patient. However, this therapy requires hospitalization and an intravenous line which does not come without risk, in addition to the risks associated with transfusions which include transfusion reactions from blood type incompatibility, antibody sensitization, and infections. Thus, the primary outcome will be to see if the number of transfusions can be reduced by administering erythropoietin.

Although the hemoglobin level, in and of itself, should not affect oxygen saturation measured by pulse oximetry, our anecdotal experience suggest that oxygen saturations in patients with cyanotic heart disease frequently improve after a blood transfusion to increase the amount of hemoglobin. Thus, the secondary outcome of oxygen saturation will be looked at for 2 reasons. First, to ensure that the treatment and control arms are similar at baseline to prevent bias for transfusions based on criteria set below. Second, to determine if our anecdotal experience has any validity.

The secondary outcome of weight gain is appropriate in the setting of infants as this variable has been used to monitor the ability to thrive and meet the body's metabolic demands. It is well established in pediatrics that the neonate and infant should gain 15-30 grams per day for optimal growth. Infants who are cyanotic, already have a deficiency in meeting their metabolic demands due to a reduced oxygen carrying capacity. This is further complicated in the instance of anemia. Thus, infants may have an increased ability to optimize weight gain in the setting of normal, stable hemoglobin levels which may be achieved with erythropoietin.

Often, cyanotic congenital heart defect neonates have prolonged initial hospital stays due to the inability to maintain acceptable oxygen saturations, and transition to adequate oral intake for appropriate weight gain. If the hospital stay is found to be shortened after starting erythropoietin, this may be of clinical and financial significance.

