Informed consent will be obtained by one of the research study members after the initial surgical or catheterization procedure. Each member is well informed of the study objectives, procedures, risks, benefits, physiology of the disease process and mechanism of how the treatment works. The informed consent will be obtained from the patient's parent in a private setting. Details of the study will be presented, and ample time will be given to answer any questions. The parent will have until the eligibility period expires based on the exclusion criteria outlined above to be included in the study. Consent will be obtained in the primary language of the parent. English and Spanish versions of the consent documents will be available and official translators will be used as appropriate. An appropriate official translator will be used during the entire duration of the participant in the study. Informed consent and HIPPA authorization will be documented with the study forms that have been drafted and approved for use in the study and will be kept in a master research file for the duration of the study in a secure area, in a locked drawer by the study team. It will be made clear to the parents that participation in the study is voluntary and that decision to be included or excluded will not compromise the standard of care that the patient deserves. Patients who meet all inclusion criteria except the hematocrit of <40% will be approached and consented, but will not be formally enrolled and randomized into a study group (control or EPO) unless their hematocrit reaches <40% during their eligibility period.

2.d Randomization Method

Study subjects will be randomized 1 to 1 by an algorithm determined by the biostatistician involved. After a study subject has been enrolled into the study, a 2-digit number (1-60) will be assigned. Based on the subject number and predetermined randomization provided, a research pharmacist will dispense the study drug if the subject is enrolled in the intervention arm. This study will not be blinded.

2.e Risks and Benefits

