There is low risk to the patient in regards to side effects of erythropoietin. In general, neonatal population studies have not shown to have significant serious side effects. Blood counts will have to be monitored to observe for polycythemia as this would increase the risk for blood viscosity and thrombosis. There are rare instances in the adult literature with development of Pure Red Cell Aplasia, which is not evident in the neonates. There is some discomfort with the injections, however this is of minimal risk. Lab draws will be done as part of a routine basis. The benefits to receiving this medication are that it may decrease the need of transfusions and hospitalizations in the period prior to a more definitive surgery.

2.f Early Withdrawal of Subjects

As this is a voluntary research study, study subjects will be allowed to withdraw from the study before completion at any time. If a withdrawal occurs before initiation of the intervention, the subject will be excluded from the study.

2.g When and How to Withdraw Subjects

A family may wish to withdraw the study subject from the study at any time. When the decision to withdraw is made after discussions with the clinical staff, a member of the research team will be notified. The date, time, and reason of the withdrawal should be noted by the research member and entered into the database. Families will be approached for permission to follow the course of the patient through the proposed study period even if the intervention was stopped.

2.h Data Collection and Follow-up for Withdrawn Subjects

Families will be approached for permission to follow the course of the patient through the proposed study period even if the intervention was stopped. An intention to treat analysis will be applied to the study subject pertaining to the research arm assigned.

2.i Blood transfusion guidelines

Absolute indications:

- Hematocrit <30%

Relative Indications:

- Hematocrit <40% AND one of the following
 - Clinical acidosis
 - Low oxygen saturations (<75%) in room air
 - Requires supplemental oxygen
 - Requires respiratory support (Ventilator, positive pressure)

When a transfusion is needed, a 10 ml/kg aliquot volume should be given.

E3 Study Drug

3.a Description

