- Age/adjusted age
- Weight
- Oxygen saturation
- Compliance of medication
- Complete blood count
- Transfusions needed
- Hospitalizations
- Adverse events (Severity, expectedness, and relationship)

G Statistical Plan

G1 Sample Size Determination and Power

This will be a randomized controlled single center prospective study of up to 60 patients to account for drop out rate. There will be a minimum 20 treatment patients and 20 control patients enrolled. This sample size is based on a 2 proportion population formula with the assumption that without treatment about 80% of infants need transfusions (based on our experience), and 40% of infants with erythropoietin will need transfusions.

G2 Interim Monitoring and Early Stopping

Unforeseen inaccuracies in design assumptions, in particular having to do with the number of infants who need transfusions without treatment could lead to decreases in the trial's statistical power to detect treatment effects. Accordingly, an analysis will be conducted to estimate the variance of the estimated difference, between the two arms in regards to number of transfusions. This analysis will be conducted within the intention-to-treat framework under which the primary analysis of the primary endpoint will be conducted.

To allow time for corrective action if necessary, this analysis will be performed approximately after 10 patients have been enrolled in both arms. If necessary, this method will be used to obtain a recommended increase in sample size.

An interim analysis of futility will also be performed to determine if the study should continue. This will be done when 10 subjects in each arm have completed the study. The study will be terminated if there is no absolute decrease in number of transfusions per subject.

It is possible that the DSMB may consider it necessary to stop the trial early due to safety concerns. To monitor safety, adverse event rates will be compared between the two trial arms and reported to the DSMB.

In addition, the research team will perform an analysis after the first 5 subjects have completed at least 1 intervention in the EPO arm for safety. These 5 patients will serve as a safety population study.

An interim analysis of safety will be done after 10 patients have enrolled and completed each arm to assess any differences in adverse events between the 2 arms. This will be reviewed by the DSMB who will make the determination as to whether any safety concerns mandate early trial termination.

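### Looking at baseline saturation cannot secure balance or prevent bias, and the transfusion analysis makes no use of it; prespecifying it as a covariate is a cheap improvement

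*Combined protocol and SAP*

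**What the plan says.** C3 states the purpose of examining saturation as follows: "First, to ensure that the treatment and control arms are similar at baseline to prevent bias for transfusions based on criteria set below". The criteria it points to are in E2, 2.i (blood transfusion guidelines). There, a hematocrit below 40% together with any one of four further items is a relative indication, and one of the four is "Low oxygen saturations (<75%) in room air".

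On design, E2, 2.d says "Study subjects will be randomized 1 to 1 by an algorithm determined by the biostatistician involved". No stratification or minimisation on saturation is described, and the trial is unblinded. G1 sets the size: "There will be a minimum 20 treatment patients and 20 control patients enrolled", within a "prospective study of up to 60 patients to account for drop out rate".

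On analysis, G4 describes the main efficacy comparison thus: "we will compare the number of blood transfusions (one 10 ml/kg aliquot = 1 transfusion) between the two groups with a two-proportion z test". No covariate is named. Saturation appears elsewhere in G4 only as an outcome: its change from baseline to 6 weeks is compared by t-test, and its trend by a mixed model. No section gives a test, a threshold or a follow-up action for the baseline comparison that C3 describes. F2 and Tables 1 and 2 have saturation recorded at baseline in both arms.

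**The concern.** C3 claims a protection that the analysis plan does not deliver. Balance comes from randomisation, and in a trial this small randomisation leaves room for chance differences. If one occurs, looking at it changes nothing, because the z test on transfusions takes no account of it.

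Saturation is a plausible driver of the primary outcome under the protocol's own rules. Entry requires a hematocrit below 40%, so at enrolment every infant already meets the hematocrit half of the relative indication, and a low saturation can complete it. C3 itself recognises that unequal saturation could bias transfusions.

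At stake is how the result of the trial actually run is reported: a transfusion difference could be presented as protected against unequal baseline saturation when nothing in the analysis protects it.

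**Working it through.** **Inputs.** From G1: 20 per arm (minimum), 30 per arm (half of the maximum of 60), transfusion rates of 80% (control) and 40% (EPO). From G4: alpha 0.05; sidedness is not stated, so two-sided is assumed. The endpoint is taken as the proportion of infants transfused, which is what G1 and a two-proportion test imply. Assumed, because the documents give no figure: a logistic relation with an odds ratio for transfusion of 1.5, 2 or 3 per SD lower baseline saturation. For false-positive rates, both arms are set at 60%, the midpoint (80 + 40)/2.

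**1. The plan's own figures.** G4 claims "80% power at the $\alpha = 0.05$ level to detect an effect size equal to 0.91 times the common standard deviation" with 20 per group. The noncentral t calculation gives 0.909, which agrees. For 80% against 40%, the unpooled formula gives 0.40/√((0.16 + 0.24)/20) = 2.83, and Φ(2.83 − 1.96) = 81%, consistent with the stated 80%. The usual pooled z test has 75% power (75.2% by formula, 75.3% exact). The 75% is the reference in step 4.

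**2. How often chance imbalance occurs.** In SD units, the standard error of a baseline difference is √(2/n).
- n = 20: √(2/20) = 0.316; 0.5/0.316 = 1.58; 2 × P(Z > 1.58) = 11.4% (12.2% with the SD estimated).
- n = 30: √(2/30) = 0.258; 0.5/0.258 = 1.94; 2 × P(Z > 1.94) = 5.3% (5.8% with the SD estimated).

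**3. What a moderate imbalance does to the unadjusted result.** Take observed imbalances of 0.4 to 0.64 SD at 20 per arm. The upper end, 2.024 × 0.316 = 0.64, is where a two-sided 5% t-test would begin to flag the difference. It is used only to mark out moderate imbalances, since the plan sets no threshold. About 16.3% of trials fall in this range, half in each direction, so about 8% favour EPO.

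A hand check of the shift at about 0.5 SD is 0.6 × 0.4 × ln(OR) × 0.5, giving 4.9, 8.3 and 13.2 points. This overstates the shift at larger odds ratios, because averaging over infants flattens the logistic curve. Simulation with no EPO effect gives:

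| Assumed odds ratio per SD | 1.5 | 2 | 3 |
|---|---|---|---|
| Shift in transfusion difference, imbalance favouring EPO (points) | 4.6 | 7.2 | 10.2 |
| False EPO claims in those trials (nominal 2.5%) | 4.3% | 5.7% | 7.1% |
| False EPO claims in the mirror-image trials | 1.1% | 0.5% | 0.2% |

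Repeat runs gave up to 7.4% at an odds ratio of 3. Over all trials, two-sided type I error is 4.8% to 4.9%.

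**4. What adjustment does.** With baseline saturation as a covariate (least squares, transfused yes/no on arm and saturation), the shift in the same trials falls to between 0 and 0.5 points and the false EPO rate returns to about 2.5%. At 80% against 40% and 20 per arm, power is 76%, 79% or 83% for the three odds ratios, against 75% unadjusted. With no association, about 1 point is lost.

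**The case against.** **The unadjusted test is not wrong.** This stands. Randomisation makes it valid on average. The raised error rate belongs to about 8% of trials and is offset by a lower rate in another 8%. Even at an odds ratio of 3, the excess false EPO claims from the affected trials amount to about 8% × (7.1% − 2.5%) = 0.4% of all trials. A reader might infer that the primary analysis is biased or invalid; nothing in the design supports that.

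**The protocol plans no baseline significance test.** This also stands. C3 says only that saturation will be looked at, and G4's t-test concerns change to 6 weeks. A reader might nevertheless apply t-test power and conclude that the check misses a 0.5-SD imbalance two times in three (power 33.8% at 20 per arm). That figure should not be used. It is power against a true population difference, which randomisation sets to zero, for a test the documents never name.

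**The association is assumed, and saturation is one criterion among several.** This is fair. Low saturation is one of four relative criteria, needs a hematocrit below 40%, and sits beside an absolute indication based on hematocrit alone. It is applied over 14 weeks, so the baseline value is an indirect predictor. Hence the range of odds ratios and the no-association case. Baseline hematocrit might also be argued for as a covariate; saturation is taken here because C3 names it as the source of bias.

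**Baseline saturation is used somewhere.** It enters the analyses of saturation itself. The gap concerns the transfusion analysis only.

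**Conclusion.** The point holds as a mismatch between C3 and G4. C3 credits a baseline comparison with securing similarity and preventing bias. The comparison can do neither, and the transfusion analysis is the same whatever it shows. This does not depend on any assumed association.

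The size does. Under odds ratios of 1.5 to 3 per SD, moderate imbalance moves the transfusion difference by about 5 to 10 points in the trials where it occurs, and adjustment removes nearly all of that. The power gain over the z test runs from 1 point (odds ratio 1.5) to 8 points (odds ratio 3), with about 1 point lost if there is no association. These figures are for the minimum of 20 per arm; imbalances above 0.5 SD are about half as frequent at 30 per arm. This is a worthwhile, low-cost improvement to a valid analysis.

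**What to change.** - **C3:** replace the claim that the comparison secures similar arms and prevents bias with a plain statement that baseline saturation will be summarised by arm (mean, SD, number below 75% in room air), without a significance test or a conclusion of similarity.
- **G4:** prespecify baseline saturation as a covariate in the primary comparison of the proportion transfused. Name the model in advance and report an adjusted risk difference with its confidence interval, whether or not the arms look balanced. Keep the unadjusted z test as a supporting analysis.

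Fixing this in advance also removes any discretion to adjust after seeing data in an unblinded trial.

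**Cost:** wording in two sections and no new data, since saturation is already recorded at baseline in both arms. Statistically, it costs one degree of freedom with 40 infants and about 1 point of power if saturation turns out not to predict transfusion. The headline estimate becomes a model-based one, slightly less direct than a raw difference in proportions.
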